2.7 Study setting

A single-centre study, conducted at The Royal London Hospital, Barts Health NHS Trust.

3.0 Patient Evaluability and Replacement

3.1 Target Accrual

36 patients aged 18 years and over admitted to the Adult Critical Care Unit at The Royal London Hospital, Barts Health NHS Trust (27 participants randomised to Omegaven arm and nine participants randomised to standard care).

3.2 Participant identification

Potential participants accepted for admission or admitted to Adult Critical Care at Royal London Hospital will be screened by the direct care team at the site. In this trial, the member of the research team conducting the screening activity will be considered as part of the direct care team in accordance with local hospital policy. All patients that undergo screening and meet the eligibility criteria will be recorded on the screening log. Only anonymised screening data will be collected by the central trial coordinating team for publication purposes. Once the patient has been randomised they will also be recorded on the study enrolment log.

4.0 Informed consent procedures

Informed consent will be obtained prior to the participant undergoing trial specific procedures at a participating site. All consent procedures will be documented in detail in the patient's medical notes. The consent procedure is the same for patient's randomise to the standard of care arm or the intervention arm.

Patients admitted to critical care are frequently unable to consent for themselves due to severity of illness, neurological impairment, sedation, delirium, trauma, etc. Similarly, having a relative in an emergency clinical situation often causes profound distress for the next of kin of the patient. It would be unethical and inappropriate to add to this stressful and emotional situation by asking them to make a decision on trial enrolment on behalf of the patient. Therefore, in cases where a patient is unable to provide consent, HIPPO will adopt a "research with delayed patient consent" model, where eligible patients will be enrolled initially through written informed consent from a Professional Legal Representative (independent clinician with clinical responsibility for patient care not involved in the trial). After professional consent is received, and the patient still does not have the capacity to consent, then a Personal Legal Representative (a family member, partner or close friend) will be approached. This is an

accepted model of consent in adult emergency and critical care research where participants are likely to lack capacity to consent and where the distress and burden on the Personal Representative should be minimised.³⁷ This model is used in a variety of other studies recruiting patients from the Adult Critical Care Unit. ³⁷⁻³⁹

The Principal Investigator (PI) has overall responsibility for the informed consent of participants at their site and will ensure that any person delegated responsibility to participate in the informed consent process is duly authorised, trained, and competent to participate according to the ethically approved protocol, principles of Good Clinical Practice (GCP), and Declaration of Helsinki. If delegation of consent occurs, then details will be provided in the site delegation log. Delegation can only be to members of the research team (which include research nurses, doctors).

Immediate patient informed consent:

If patients have full capacity as deemed by the treating clinician to be able to give fully written informed consent they will be approached directly by a delegated member of the site research team. This process will include provision of the PIS accompanied by the ICF, and an explanation of the trial. Patients will be given up to 36 hours depending on the time of approach (as intervention needs to start within 48 hours of adult critical care admission) to make an informed decision. If patients feel they are unable to make an informed decision during this timeframe they will not be included in the trial.

If a participant is unable to read or sign the informed consent form but has full capacity to give consent, this can be provided on the participant's behalf by a witness. A statement will be included in the consent form explaining that the participant understood the information and informed consent was given freely.

Delayed patient consent procedure:

Professional Legal Representative consent

A Professional Legal Representative will be approached in order to obtain informed consent on behalf of the patient. The Professional Legal Representative will be fully informed about the trial by a member of the research team. They will be given a copy of the Professional Legal Representative Information Sheet and sign a Professional Legal Representative Consent form. If the Professional Legal Representative declines participation of the patient, no further attempts for consent will be made. If the Professional Legal Representative withdraws the patient, the trial treatment will be stopped (if ongoing) immediately. Data collection from

medical notes review will continue unless the Professional Legal Representative declines. Blood samples and data collected up to this point will be retained.

Personal Legal Representative consent

As soon as appropriate and after Professional Legal Representative consent, the Personal Legal Representative will be approached if available and fully informed about the trial by a member of the research team. They will also receive a copy of the Personal Legal Representative Information Sheet. Judgement on when the approach is appropriate is situation dependent and will be made by the PI or the Research Nurses. The Personal Legal Representative will also be informed that the patient has currently been enrolled in the trial through Professional Legal Representative Consent and they will be asked to provide their opinion on whether the patient would object in taking part in medical research. If the Personal Legal Representative decides that the patient would not object to taking part in research, they will provide consent either written or via a witnessed phone consent.

If a Personal Legal Representative advises that, in their opinion, the patient would choose not to participate in the trial, the trial treatment will be stopped (if ongoing). Data collection from medical notes review will continue unless the Personal Representative declines. Blood samples and data collected up to the point of withdrawal will be retained.

If no Personal Legal Representative can be approached, or they feel unable to make a decision, the Professional Legal Representative Consent will remain in place until the patient regains capacity. This will be documented in the patient's medical record.

Patient informed delayed consent

The patient will be informed of their participation in the study as soon as possible when they have return of full capacity to provide informed delayed consent. It is anticipated that this first approach will occur within 24-48 hours of regaining capacity during their hospitalisation at The Royal London Hospital, however this will depend on the patient's condition and will be left to the discretion of the clinical team. This process will include provision of a PIS accompanied by the ICF, and an explanation of the trial. Participants will have time to consider their ongoing participation, to discuss with friends and family and to have their questions answered. The participant will then be asked whether or not they would like to continue participation in the study. If they decide to participate, the patient will sign a copy of the ICF.

If participants decline to continue participating in the trial, treatment will be stopped (if ongoing), and all blood samples and data collected up to the point of withdrawal will be retained. Data collection from medical notes review will continue unless the participant declines.

If the patient does not regain capacity during their stay at The Royal London Hospital and is transferred to another hospital without providing consent, a covering letter notifying them of their participation in the trial, PIS and ICF will be sent with their medical notes. The letter will direct the patient to the PIS for detailed information on the trial and provide contact details if the patient wishes to discuss the trial further. A prepaid return envelope will be included to receive the signed ICF. If no response is obtained from the patient, the 30-day follow-up phone call will be conducted, and the participant will be asked at this time to confirm their willingness to participate, and if so, to return the consent form or provide witnessed telephone consent. If no consent is received, blood samples and data that has already been collected will be retained under the Legal Representative Consent.

For those patients that have regained capacity and were discharged before being approached by the research team, they will be contacted by phone in the first instance. If the research team does not get a response to the phone call, the patient will be approached by post. In either case, the patient will be sent a covering letter and a copy of the PIS and ICF. The letter will direct the patient to the PIS for detailed information on the trial including contact details if they wish to discuss the trial further. A prepaid return envelope will be included to receive the signed ICF. If no response is obtained from the patient, the 30-day follow-up phone call will be conducted, and the participant will be asked at this time to confirm their willingness to participate, and if so, to return the ICF or provide witnessed telephone consent. Additionally, the letter will also confirm that if no consent is received within four weeks from the time of the letter being sent, then the participant's data will be included in the trial under the Legal Representative Consent and no further contact will be attempted.

Patients will be given the opportunity to opt out of on-going data collection. A decision to opt out during the telephone call will be documented in the patient's medical records by the person seeking consent. This will also be recorded on the eCRF. For the postal approach, the patient can actively opt out by returning the consent form declining participation or using the telephone contact details provided on the PIS, at any point during the trial.

Consent considerations:

The right of a participant to refuse participation without giving reasons will be respected. There will be no financial penalty, and the participant will continue to receive their treatment as standard care without prejudice. If the participant decides to withdraw from the study, further information about next steps can be found in section 9. This will be clearly specified in the PIS.

A signed copy of the respective ICF will be retained by the patient or legal representative, if applicable; one copy goes in the participant's medical notes along with the PIS, and the original

will be filed in the ISF. Patients who are consented but not entered into this study should be recorded (including reason not entered) on the screening log in the ISF. The ICFs will be countersigned by the PI or medical delegate, in a timely manner, if the consent is not taken by a medical qualified person.

Where a participant is required to re-consent (for example if new Research Safety Information becomes available during the study, or following an amendment that affects the participant, or new information needs to be provided to a participant) it is the responsibility of the PI to ensure this is done in a timely manner and prior to the next dose of IMP (where applicable).

Patient withdrawal and refusal for continuous data collection will be documented in patient's medical records.

4.1 Vulnerable participant considerations

The study involves participation of vulnerable participants, as adult patients admitted to critical care are frequently not able to consent for themselves. The PI is responsible for ensuring that all vulnerable participants are protected and participate voluntarily in an environment free from coercion or undue influence. Consent procedure for vulnerable patients is described above.

4.2 Writing, reading, and translation considerations

If verbal translation is needed, an NHS hospital interpreter will be provided as per local trust policy.

4.3 Participants lacking capacity

The consent process for patients temporarily lacking capacity is described above.

5.0 Participant allocation

Since the trial involves an IMP that is unlicensed in UK, the PI or delegated doctors will be required to confirm eligibility of patients identified by the research team in the medical notes prior to approach. Following written informed consent, the patient will be randomised to either the standard care or Omegaven arm in blocks of 12 patients per dose-escalation phase. All randomised patients will be recorded on the study enrolment log with their trial ID.

6.0 Participant eligibility criteria

6.1 Inclusion criteria

- Age 18 years and over
- Patients requiring intubation and ventilation OR two or more other organ systems support (Sequential Organ Failure Assessment (SOFA) score ≥2 in >2 domains) without requiring intubation and ventilation.⁴⁰
- Patients predicted to remain in critical care for at least 72 hours as determined by the
 Intensive Care Consultant with clinical responsibility for patient care.

6.2 Exclusion criteria

We are specifically not excluding patients with acute life-threatening conditions such as collapse or shock, recent cardiac infarction, stroke, embolism, undefined coma status, severe haemorrhagic disorders or severe liver or renal insufficiency as indicated in the SmPC. We seek to test the safety of Omegaven in critically ill patients (who suffer from these conditions) as part of a new set of indications. The SmPC notes that some of these are considered contraindications as a result of lack of experience, which we seek in this safety trial to inform. In previous studies, Omegaven has been given therapeutically to critically ill patients before, in the UK ^{19 20}, and in- and outside the EU^{17 18 22 23}, but safety data are scarce. A safety trial such as the one we are proposing is necessary prior to a larger efficacy trial.

Exclusion criteria (as defined in the patient's medical notes):

- Patients requiring total parenteral nutrition at time of enrolment or during the first 10 days.
- Palliative care admission for end-of-life care or withdrawal of active therapy as determined by the Intensive Care Consultant with clinical responsibility for patient care.
- Neutropaenia (<1x10⁹/l) on admission to the Adult Critical Care Unit
- Lymphopenia (<0.25x10⁹/l) on admission to Adult Critical Care Unit
- Primary immune deficiency
- Bone marrow transplant recipient
- All immunosuppressive drug therapy (with the exception of corticosteroid use for acute illnesses in the preceding five days)
- Recorded or reported allergy to fish, or egg protein or to any of the active ingredients or excipients
- Known inborn errors of lipid metabolism

- Recorded or reported severe hyperlipidaemia or severe disorders of lipid metabolism
- Electronic health record documentation ± clinical concern and if available: serum triglycerides >400 mg/dl on admission to the Adult Critical Care Unit
- Enrolment in any other study with an IMP or a study that may have similar primary outcome
- Therapeutic anti-coagulation therapy
- Pregnancy

The absence of the above criteria in the medical notes will be considered to indicate no concern.

To verify fish or egg allergies, the electronic patient record will be checked when confirming eligibility. Clinical decision making will also be utilised. If patients are receiving standard enteral feed (Fresubin Original), containing fish oil they are deemed not to have a fish allergy. We will also talk to the clinician with clinical responsibility for patient care asking if there is any concern of an egg or other allergy from any communications from relatives or friends.

Patients in ICU are continuously monitored by the bedside nurse, who will pick up and react to possible signs of allergic reactions. Additionally, the research nurses administering Omegaven will stay at the patient's bedside and monitor the patient every 5 minutes for the first half an hour after the first administration of Omegaven, to make sure administration is of no concern.

7.0 Trial intervention

Following consent, the intervention will start within 48 hours of critical care admission and continue for 10 days or until hospital discharge, whichever is sooner. Participants will receive either standard care or Omegaven.

Standard care arm

Patients in the standard care group will be managed by clinical staff according to local policy and guidelines until hospital discharge. Standard care includes receiving enteral nutrition according to the dietitian's advice.

Intervention arm

Participants will be randomised sequentially in three dosing phases (0.2, 0.4, 0.6 g/kg/d Omegaven) according to the BOIN dose-escalation plan (**Figure 2**, and section below).^{35 41} Omegaven will be provided based on bodyweight in kg, except in cases of morbidly obese patients (actual bodyweight > 200% of the ideal bodyweight). In this case, adjusted body weight will be used for Omegaven dosing, using the following formula:

Adjusted bodyweight = ideal body weight + (0.4 x (actual body weight – ideal bodyweight)).11

Patients will receive intravenous Omegaven to be administered daily (at any time within a 24-hour period) until day 10 or hospital discharge, whichever is sooner. Omegaven will be administered via a central line if available and if this is not possible it will be given peripherally. The timing of Omegaven administration will be determined in conjunction with the direct care team to ensure intervention delivery can be integrated with direct clinical care. Omegaven will be administered by an appropriately trained and qualified member of the research team, named on the delegation log. Treatment breaks are permitted for clinical reasons, with delivery of <80% of the intervention being considered a deviation.

The infusion rate of Omegaven will be initially set at 0.5 ml Omegaven/kg body weight/hour as specified in the SmPC (maximum infusion rate). For example, a 100 kg patient receiving 0.6 g/kg/d Omegaven would require a 12-hour infusion. The rate can be reduced if there is a clinical indication (e.g. small-bore peripheral canula, or uncontrolled diabetes mellitus (defined as diabetic ketoacidosis, or hypoglycaemic hyperosmolar state, as decided by the critical care consultant with responsibility for patient care)). Further guidance will be provided in the trial specific SOP.

8. Study Schedule

8.1 Schedule of treatment and assessments for each visit

The trial intervention period will commence on the day of randomisation and finish with the 30-day follow-up.

	Within 48 hours	n 48 hours Days from start of intervention													
Assessment/ investigations	of critical care admission/ Day 1 of intervention	2	3	4	5	6	7	8	9	10	11	20	30		
Eligibility review	Х														
Patient informed consent or by Professional/ Personal Legal	x														
Representative *															
Randomisation	Х														
Omegaven administration	х	х	х	х	х	х	х	х	х	х					
DLT events and safety review	х	х	х	х	х	х	х	х	х	х	х				
Trial blood sample	X [#]				Х					Х		Х			
Follow-up in ward/telephone call													Х		
Medical record review	х	х	х	х	х	Х	Х	х	х	х	х		Х		

HIPPO V3.0 14/02/2025 Page 34 of 62

^{*} Patient consent will be obtained when the patient regains the capacity to consent

[#] before intervention begins

8.2 Trial and follow-up assessments

The following assessments will be done in all participants:

Eligibility

- Screening for inclusion and exclusion criteria
- Medical history
- Informed consent

Randomisation (within 48 hours of admission to critical care)

- Participant Initials
- Trial ID (generated automatically at the point of randomisation)

Baseline data

- Age
- Sex at birth
- Medical history

Day 1-Day 10 or hospital discharge

- IMP administration and details (intervention arm only)
- Safety review

DLT assessment

Day one continuing daily until day 11

Blood samples

- Before start of intervention (within 48 hours of admission to critical care)
- Day five from start of intervention
- Day 10 from start of intervention
- Day 20 from start of intervention; censured at hospital discharge

Routinely collected data

- Medical note review for
 - Infections
 - o Clinical Pulmonary Infection Score
 - o Antibiotic free days
 - Ventilator free days

- Mortality
- Length of critical care stay
- Length of hospital stay
- o Length of hospital stay before Adult Critical Care Unit admission
- Critical care level received
- Steroid free days
- Renal replacement therapy free days
- Enteral feed intake
- Bristol Stool Score
- SOFA score
- Laboratory values
- Blood transfusions
- Hospital admission

Follow-up phone call at 30 days

- o Antibiotic prescriptions after hospital discharge
- o Use of omega-3/nutritional supplements in the 3 months prior to hospitalisation
- Ethnicity

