15.0 Statistical and data analysis

15.1 Sample size calculation

A total of 36 participants will be recruited (randomised 1:3 control:intervention). The number of participants treated on each dose of Omegaven will be determined by the escalation / deescalation rule specified in the BOIN design shown in Figure 2 and Table 1, which aims to exclude a toxicity rate of ≥ 30%. The minimum number of participants to be treated on a single dose is nine and the maximum is 27. Assuming mortality of approximately 20-30% in critically ill patients, we will replace up to a maximum of three patients in each study phase in case of patient death, or withdrawal. There is no formal assessment of sample size required for a phase I dose escalation trial, however 36 participants (nine control and 27 intervention) will be sufficient to provide pilot data on the exploratory outcomes. A published study with eight patient samples per group enabled examination of the p38 inhibitor and identification of a doubling in proliferation and cytotoxicity as measured by granzyme and perforin expression using nine patients per group would provide almost 80% power to detect a mean difference of 12 in %CD107a CD8+ EMRA T cells (assuming SD=6 and α=0.05) (unpublished data, [name])¹⁵. Early phase trials often use less conservative type I error rates as they can be considered screening studies to inform a future definitive trial; with this sample size the trial would have 87.4% power for α =0.1 and 94.4% for α =0.2 using the parameters given above.

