15.6 Analysis of participant populations

Analyses will include all participants who receive at least one dose of Omegaven.

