15.14 Other statistical considerations

As described in section 9.0 if a patient withdraws, dies, or is excluded by their Intensive Care Consultant with clinical responsibility for patient care or the study team during the 10-day dosing period, they will be replaced. Three such patients, in case of withdrawal or death, will be replaced in each study phase.

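### Ethnicity and pre-admission supplement use are baseline characteristics but are collected only at the day-30 contact, so the baseline description will cover only survivors who can be reached

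*Protocol*

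**What the plan says.** Protocol section 8.2 opens by stating that the assessments below it are for all participants. Its baseline list contains age, sex at birth and medical history. Two further patient characteristics come at the end of the section, under "Follow-up phone call at 30 days": ethnicity, and "Use of omega-3/nutritional supplements in the 3 months prior to hospitalisation".

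The schedule in section 8.1 has one matching row, "Follow-up in ward/telephone call", with a single mark at day 30. No section names an earlier collection point, a proxy respondent or a record source for either item.

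Four other statements bear on this:
- Section 15.1 plans with "Assuming mortality of approximately 20-30% in critically ill patients".
- Section 15.14 states that "Three such patients, in case of withdrawal or death, will be replaced in each study phase".
- Section 15.6 states that "Analyses will include all participants who receive at least one dose of Omegaven", so a dosed patient who later dies stays in the analysis set.
- Section 2.4 measures the Omega-3 Index and fatty acid profile before the intervention and on days 5, 10 and 20.

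**The concern.** Both items describe the patient before randomisation, and nothing about them becomes better known by waiting 30 days. Tying them to a late contact makes their availability depend on survival, on being reachable and on capacity at day 30, all of which are determined after randomisation. The protocol itself expects a substantial share of patients to die.

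A baseline table built this way describes the patients who survived and answered. It does not describe the groups that were randomised or dosed. Ethnicity is affected as a standard descriptor. Supplement use is affected because the first exploratory objective (section 2.2) concerns the Omega-3 Index and fatty acid profile, and recent supplement intake is an obvious candidate explanation for a patient who arrives with a high value.

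**Working it through.** The protocol states no figure for missing values on these items, so there is nothing to reproduce. The size follows from the protocol's own planning numbers.

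**Inputs**
- Sample size: "A total of 36 participants will be recruited (randomised 1:3 control:intervention"), that is 9 control and 27 Omegaven (15.1).
- Mortality m: 0.20 to 0.30 (15.1).
- Replacement: up to 3 patients per phase over 3 phases, so at most 9 more patients and 36 + 9 = 45 enrolled (15.1, 15.14).

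**Assumption.** Section 15.1 gives no time horizon for the mortality figure. The calculation takes all of it to occur before the day-30 contact. Deaths after day 30 would make the loss smaller.

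**Expected number with no value because of death = N × m**

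| Group | N | m = 0.20 | m = 0.30 |
|---|---|---|---|
| All planned | 36 | 7.2 | 10.8 |
| Omegaven | 27 | 5.4 | 8.1 |
| Control | 9 | 1.8 | 2.7 |
| All, every replacement used | 45 | 9.0 | 13.5 |

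Treating deaths as independent, the exact binomial 95% range for 36 patients is 3 to 12 at m = 0.20 and 6 to 16 at m = 0.30. The chance of no death at all is 0.8^36 = 0.0003 at the lower rate, so some loss is close to certain.

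Patients who survive but are not reached, lack capacity at day 30 or opt out of data collection (section 4.0) add to these numbers. The protocol gives no rate for them, so they are not counted.

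**Use of the two items in the planned analyses**
- Primary outcome (15.4): isotonic regression on dose-limiting toxicity. Neither item enters.
- Laboratory outcomes (15.4, 15.11): repeated-measures analysis of covariance adjusted for the baseline value of the outcome, with no other adjustment. Neither item enters.
- Subgroups (15.10): none planned.

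The missing values therefore affect description and interpretation. They change no planned estimate, interval or dose decision.

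**The case against.** The strongest reply is that the blood sample already does the main job. Section 2.4 measures the Omega-3 Index and a full fatty acid profile before treatment, and section 8.2 includes that sample among the assessments for everyone, so it covers controls and patients who later die. Section 15.4 adjusts for it. This stands, and it is why the point is minor. A reader might infer that a high Omega-3 Index in a control could not be interpreted without the supplement history. The documents do not support that, because the baseline index shows whether the value was already high on entry. Only the reported reason for it is missing.

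A reader might also infer that recall of supplements will differ by arm, since the trial is open label. Section 8.4 says the care team knows the allocation. The protocol says neither that patients are told their arm nor that they are kept from knowing it. Differential recall is conjecture here, and it could not apply to ethnicity.

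A third tempting step is to take three controls per phase and compute the chance that at least one has no value: 1 − 0.8^3 = 49% or 1 − 0.7^3 = 66%. Those figures require every death to fall by day 30 and ignore replacement of patients who die during dosing, so they should not be relied on.

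Finally, there is a practical case for the present timing. Many of these patients cannot answer questions within 48 hours of admission, and section 4.0 wants the burden on relatives kept low. That explains why a day-30 question is useful as a back-up. It does not explain why it is the only source for supplement use, and it gives no reason to delay ethnicity, since medical records are reviewed from day 1 (8.1). Baseline medical history might happen to capture either item, but the protocol does not say so.

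**Conclusion.** The point holds as a minor design fault. Two pre-randomisation characteristics are scheduled where they will predictably be missing for non-survivors, in a section that presents its assessments as applying to all participants. The loss from death alone is about 7 to 11 of 36 patients, provided the assumed 20-30% mortality falls by day 30. It is smaller if some deaths come later, and larger once unreachable patients and those without capacity are added.

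The consequence is limited to an incomplete baseline description and the loss of a reported history that could account for a high baseline index. The primary outcome, the dose decisions and the adjusted laboratory comparisons are unaffected.

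**What to change.** In section 8.2, move ethnicity and prior supplement use into the baseline list, and mark them accordingly in the 8.1 schedule.

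- **Ethnicity:** take it from the medical record, which is already reviewed from day 1.
- **Supplement use:** ask the patient at consent if they have capacity. Otherwise ask the patient on regaining capacity, or the representative at the existing step in section 4.0, where "the Personal Legal Representative will be approached if available and fully informed about the trial by a member of the research team", at a time judged appropriate.
- **Day-30 contact:** keep it to fill gaps only.
- **For each value:** record the source (patient, representative or record) and the date.

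The cost is two case report form items moved, with source and date fields added. Some supplement histories will be proxy reports, representatives face one more question, and some values will still be missing where no representative is available. No sample size, dose rule or analysis changes.
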